Secondary Objectives	 To compare the HPV oropharynx prevalence between different sites—in order to identify the different reservoirs of HPV infection To describe the distribution of HPV seropositivity in the study population by age and gender To describe HPV-type distribution overall by age, gender, and sampling site To describe distribution by age and gender of patients who are both HPV PCR positive and anti-HPV L1 sero-positive – predicting persistent HPV infection To provide preliminary estimates of the clearance and persistence of HPV infection and antibodies in the oropharynx, as detected in follow-up oral fluid, finger tips/nail brushings and urine samples To assess the presence of anti-L1 HPV antibodies in saliva as a marker of vaccination or previous infection in the oral cavity To assess the presence of HPV in the urine To assess the presence of HPV in finger tips/nail brushings To provide preliminary evaluation of the performance of potential non-invasive tests for the detection of HPV infection in the mouth against HPV detection rates in tonsillectomy and oropharyngeal scrapes To identify the change in overall prevalence and distribution of HPV in tonsils over time, and to describe preliminary data on age and gender specific changes over time To provide preliminary data on the potential effect of HPV vaccination in the prevention of oral infection
Duration	6 months setup and pilot, recruitment over 36 months and 12 months for analysis
Population	Prospective cohort of up to 1000 eligible patients (minimum set of samples) undergoing tonsillectomy and a historical comparison group of 1250 patients who underwent tonsillectomy in early 2000's
Eligibility	 Inclusion criteria for prospective cohort: The following patients are eligible: Patients undergoing tonsillectomy for non-cancer reasons including operations for: recurrent tonsillitis, snoring surgery or obstructive sleep apnoea Age 0 to 65 years Patient or parent(s)/legal guardian(s) has given written informed consent/assent

	Exclusion criteria:
Eligibility	The following patients are not eligible to join the study: Patients undergoing adenoidectomy alone with no tonsillectomy Patients with previous oropharyngeal cancer or oral cancer, or any other head and neck cancer such as nasopharyngeal or laryngeal cancer that is currently undergoing or previously has been diagnosed or treated Learning disability preventing an adult over 16 years old from giving their own consent

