12.2. ANALYSIS OF OUTCOME MEASURE

The statistical analyses will be described in detail in a statistical analysis plan (SAP). All of the tests will be two-sided with an alpha level of 0.05.

12.2.1. PRIMARY OUTCOME:

The overall prevalence will be estimated as the number of patients with HPV detected in tonsils divided by the total number of patients with available samples. An exact 95% confidence interval will be computed. The prevalence per age and gender group will be calculated similarly.

The relationship between prevalence and age will be explored using logistic regression with the age as a continuous covariate and gender and centre as categorical covariate. The number of degrees (one, two, three) of the model and possible variable transformation (e.g. log-transformation of age) could be determine based on graphical analysis of prevalence versus age relationship and on model fit criteria (e.g. AIC).

12.2.2. SECONDARY OUTCOME:

The overall prevalence will be estimated as the number of patients with HPV detected in oral fluid, oropharyngeal scrapes and urine samples divided by the total number of patients with available samples. An exact 95% confidence interval will be computed.

The prevalence per age and gender group will be calculated similarly. Prevalence rate will be compared among centres using a Cochran-Mantel-Haenszel test with stratification by age group.

Relationship between the prevalence of HPV in tonsils and the prevalence of HPV in oropharyngeal scrapes, oral fluid, and urine samples will be analysed by computing kappa coefficient. Specificity, sensitivity, positive predictive value and negative predictive value of HPV detection in the different sample types will be derived using the oral sample results as the reference.

Relationship between presence of anti-HPV L1 antibody in oral fluid samples and occurrence of HPV in tonsils and/or in oropharyngeal scrape samples will be analysed by computing kappa coefficiency. Specificity, sensitivity, positive predictive value and negative predictive value of anti-HPV L1 antibody assay will be derived using the oral sample results as the reference.

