12.3. SAMPLE SIZE CONSIDERATIONS

An analysis of current literature suggests that in a population recruited between 1990 and 2000, the prevalence of oral HPV was about 6.5%, varying from 0% - 10%. However, in an analysis of oropharyngeal scrapes and oral washings, the prevalence of HPV detection was much higher at 31%.

Pilot data of patients having tonsillectomy at University Hospital Coventry over two 3-month time periods are shown below in table 3. The number of tonsillectomy operations performed at the Heart of England NHS Foundation Trust - is approximately 50% of that for University Hospital Coventry quoted below.

Table 5: The number of tonsillectomy operations performed at University Hospital Coventry.

Age Group*	Number of Monthly recruitment (%)		
0-4	7 (12%)		
5-9	12 (20%)		
10-14	7 (12%)		
15-19	10 (17%)		
20-24	6 (10%)		
25-29	5 (8%		
30-34	4 (7%)		
35-39	5 (8%)		
40-44	1 (2%)		
45-49	1 (2%)		
50-69	1 (2%)		
Total	59		

^{*}There was an equal distribution of males and females in the group.

We plan to enrol 925 patients. The precision of the overall prevalence estimate that would be achieved with such a number is summarised in Figure 1 for prevalence ranging from 1 to 31 %. For example, if the observed prevalence is 10 %, the 95 % confidence interval for the overall population will be 8.4 to 11.8 % corresponding to a relative precision of 17 %.

[figure not shown]

Figure 1: Precision (95% confidence interval) of the prevalence estimate versus the prevalence observed in a random sample of 1250 patients.

We will also undertake a stratified sampling strategy to allow comparisons between those aged 14 and under (non-exposed, approximately one third of the cohort), and patients over 14 years of age (exposed) to allow the determination of the age of acquisition of infection and the optimal age of start of vaccination. The stratified sampling strategy will recruit patient subgroups as follows:

Table 6: The stratified sampling strategy for patient recruitment.

Age group	Sample size (%)		
0-4	150 (16.5%)		
5-9	150 (16.5%)		
10-14	150 (16.5%)		
15-19	150 (16.5%)		
20-24	150 (16.5%)		
25-34	100 (11%)		
35-44	60 (5.5%)		
45-65	15 (1.0%)		
Total	925		

[figure not shown]

Figure 2: Precision (95% confidence interval) of the prevalence estimate versus the prevalence observed in a random sample of 100, 150, and 250 patients.

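### The precision quoted for the primary prevalence estimate (8.4 to 11.8 %, relative 17 %) belongs to 1250 patients, not the 925 planned; two other figures in section 12.3 also do not fit Table 6

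*Protocol*

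**What the plan says.** All of the sample size reasoning for the primary objective is in protocol section 12.3.

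- The target: "We plan to enrol 925 patients". Table 6 allocates these patients to eight age groups and also totals 925.
- The link from target to precision: "The precision of the overall prevalence estimate that would be achieved with such a number is summarised in Figure 1".
- The worked example: "if the observed prevalence is 10 %, the 95 % confidence interval for the overall population will be 8.4 to 11.8" %. The relative precision given with it is 17 %.
- The Figure 1 caption: "Precision (95% confidence interval) of the prevalence estimate versus the prevalence observed in a random sample of 1250 patients".
- The share aged 14 and under: "non-exposed, approximately one third of the cohort".
- The Figure 2 caption gives precision curves for samples of 100, 150 and 250.

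Section 12.2.1 fixes the interval method for the primary outcome: "An exact 95% confidence interval will be computed". The Population row of the Study Summary gives an upper figure: "Prospective cohort of up to 1000 eligible patients (minimum set of samples").

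**The concern.** The text attaches the worked interval to 925 patients, while the caption of the figure it cites names 1250. Both cannot be right for one interval at one prevalence, because the width depends on the number of patients.

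The point matters because precision is the only sample size justification given for the primary objective. The power calculation in section 12.4 serves the comparison with the historical cohort, which is a secondary objective. An ethics committee, funder or reader relying on section 12.3 would credit 925 patients with the precision of a cohort about a third larger (1250/925 = 1.35).

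The age split matters for a related reason. Section 12.3 uses the comparison of patients aged 14 and under with older patients to address age at acquisition and the age at which vaccination should start. The stated share describes how that comparison is built, and it does not agree with the recruitment table beside it.

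**Working it through.** **Inputs.** Planned enrolment 925, observed prevalence 10 %, stated interval 8.4 to 11.8 %, stated relative precision 17 %, caption size 1250 (all section 12.3); exact 95 % interval (section 12.2.1); ceiling of 1000 (Study Summary).

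**Formulas.** For x positives among n patients, the exact (Clopper-Pearson) limits are

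- lower = 2.5 % quantile of Beta(x, n − x + 1)
- upper = 97.5 % quantile of Beta(x + 1, n − x)
- half-width = (upper − lower)/2
- relative precision = half-width/(x/n)

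**Step 1: reproduce the protocol's figure.** With n = 1250 and x = 125, the limits are 8.39 % and 11.80 %. The half-width is (11.80 − 8.39)/2 = 1.70 points, and 1.70/10 = 17.0 %. All three stated figures are matched.

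**Step 2: the same calculation at other sizes.** Ten per cent of 925 is 92.5, which cannot be observed, so both neighbouring counts are shown with the interpolated value.

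| n | x | Exact 95 % CI | Half-width (points) | Relative precision |
|---|---|---|---|---|
| 1250 | 125 | 8.39–11.80 % | 1.70 | 17.0 % |
| 1000 | 100 | 8.21–12.03 % | 1.91 | 19.1 % |
| 925 | 92 | 8.09–12.06 % | 1.98 | 19.9 % |
| 925 | 93 | 8.19–12.17 % | 1.99 | 19.8 % |
| 925 | 92.5 (interpolated) | 8.14–12.12 % | 1.99 | 19.9 % |

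**Step 3: could another method or rounding explain it?** At 925, with 92 or 93 positives:

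- Wald: 8.0–11.9 % or 8.1–12.0 %
- Wilson: 8.2–12.0 % or 8.3–12.2 %
- Jeffreys: 8.1–12.0 % or 8.2–12.1 %
- Agresti-Coull: 8.2–12.1 % or 8.3–12.2 %

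None gives 8.4 to 11.8 %, and the relative half-width is about 19.3 % or more in every case. Working backwards, the exact method rounds to 8.4–11.8 % at 10 % prevalence only for n from 1186 to 1314. Among the other methods, the smallest n that gives the stated interval is 1132 (Jeffreys).

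**Step 4: share aged 14 and under.** Table 6 has 150 patients in each of the groups 0–4, 5–9 and 10–14. That is 3 × 150 = 450, and 450/925 = 48.6 %. One third of 925 would be about 308.

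**Step 5: Figure 2 sizes.** The stratum sizes in Table 6 are 150 (five strata), 100, 60 and 15. The caption's 100 and 150 each match a stratum; 250 matches none.

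**The case against.** The strongest reply is that the error is small and harmless to the results. The half-width rises by about 0.3 of a percentage point. The primary objective is estimation: section 12.3 sets no precision threshold and section 12.2 ties no decision to the primary estimate, so no target is missed. The published interval will be computed by the exact method from the patients actually observed. All of this stands. It limits the weight of the point but does not make the printed figure right for 925.

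A reader might be tempted to infer more than the protocol supports:

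- **That relative precision becomes much worse at realistic tonsil prevalences.** Summing the studies in Table 2 gives 30/978 = 3.1 %, where relative precision would be about 38 % with 925. With 1250 it would already be about 32 %, so most of the fall from 17 % comes from the lower prevalence, not from the change in n. The pooled figure is also a poor planning value: Table 2 is titled for high-risk types, whereas the primary outcome is any HPV in tonsil, and its studies range from 0 to 7.8 %. The 10 % case is offered only as an example, and Figure 1 is said to cover 1 to 31 %.
- **That the Study Summary sets a conflicting third target.** Up to 1000 is a ceiling, and 925 lies within it. It does not rescue the stated interval either, since 1000 gives 8.2 to 12.0 %.
- **That Figure 2 is deficient because it has no curves for the strata of 60 and 15.** The protocol does not say the figure covers every stratum. The sizes 100 and 150 cover six of eight strata, 850/925 = 92 % of patients. Only the 250 curve has no counterpart.

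**Conclusion.** The stated precision is wrong for the stated sample size. At 10 % prevalence, 925 patients give an exact 95 % interval of about 8.1 to 12.1 % and a relative precision of about 20 %, against the printed 8.4 to 11.8 % and 17 %. The printed figures are those of 1250 patients. The loss is modest, about 2.0 against 1.7 percentage points of half-width, and the validity of the final estimate is not affected. In the same section, about one third aged 14 and under should be about half (48.6 %), and the n = 250 curve in Figure 2 corresponds to no planned stratum.

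The calculation treats the cohort as a simple random sample, as the Figure 1 caption does. A prevalence reweighted for the age-stratified recruitment could have different precision. It also assumes that all 925 patients contribute a tonsil result. Section 12.2.1 divides by patients with available samples, so any shortfall would widen the interval further. The amendment table records a change of recruitment target in version 5.0, which may explain the mismatch, but the conclusion rests only on the current text of section 12.3.

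**What to change.** In section 12.3:

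1. Restate the worked example for 925 patients as about 8.1 to 12.1 %, with a relative precision of about 20 %, marked as approximate because 92.5 positives cannot occur (92/925: 8.1–12.1 %; 93/925: 8.2–12.2 %).
2. Redraw Figure 1 for 925 and correct its caption.
3. Change the description of those aged 14 and under from approximately one third to approximately half of the cohort.
4. Replace the n = 250 curve in Figure 2 with stratum sizes taken from Table 6.

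The cost is wording and two redrawn figures. The stated precision becomes slightly less favourable, and no extra patients are needed. Bringing the age split into line by altering Table 6 instead would change the recruitment strata. That is a design change, is not part of this correction, and would cost more than is described here.

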1.2. CAUSE OF THE PROBLEM

The rising incidence in Europe and the USA has recently been attributed to a new distinct disease entity called Human Papillomavirus-related oropharyngeal squamous cell carcinoma (HPV-OPSCC), caused by the Human Papillomavirus (HPV), which also causes most cervical and anal cancers (Mehanna, 2010). HPV infection is sexually-transmitted, and in the mouth may be linked to oral sex. Other bodily fluids e.g. saliva may potentially also be routes of transmission, especially before the onset of sexual activity. A meta-analysis of the world literature performed by our group shows that the proportion of HPV-OPSCC has more than doubled in Europe and the USA over the past decade (rising from 35% to 73% in Europe for example). Incidence in Europe and the USA is expected to continue to rise significantly due to the lag time between HPV infection and disease presentation (~25 yrs.), prompting concerns by some experts of an epidemic of viral-induced malignancy (Sturgis 2010).

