1.4. GAPS IN THE LITERATURE

The vaccination of girls only may not protect males, especially if herd immunity is not achieved due to incomplete uptake of the vaccine in girls. Therefore, in view of the recent rise in HPV-oropharyngeal carcinoma, some experts are raising the possibility of the vaccination of boys as well as girls. Yet, to date insufficient data is available on oropharyngeal HPV infection to allow the accurate assessment of the need for and cost effectiveness of including boys in the HPV vaccination programmes in the EU.

Furthermore, there is little information on the prevalence of HPV infection in the mouth in the general population or on the age and gender distribution of this infection. The data that is available consists of small studies. These are usually retrospective and most of the study cohorts are over ten years old – therefore most of the prevalence data available is at least ten years old. Furthermore, the studies used a variety of sample types and different HPV detection techniques. Therefore the results are widely varying with reported HPV prevalence rates in the mouth between 0% and 31%.

Table 1: Frequency with which high-risk HPV types were detected in oral exfoliated cell samples using PCR methods (> 10 cases).

Study	City	Period of patient accrual	Age range	HPV detection	Type of oral sample	No of samples	HPV+ rate
D'souza 2007	Baltimore, USA	2000-5	<50yrs-34%, >50yrs-66%	PCR	Oral rinse and brush	200	6%
Smith 2007	Iowa , USA	n/a	2-20	PCR	Oral exfoliated cells	1235	1.9%
Rintala 2006	Finland	N/A	28	PCR	Scrapings	462	15-27%
Smith 2004	Iowa, USA	1994-97	18-70, 34% <55	PCR	Oral exfoliated cells	333	10.8%
Summersgill 2001	Iowa	<2001	<20	PCR	Swabs or oral rinses	268	8.7% <7yrs, 0% 7-12, 5.2% 13-20
Koch 1997	Denmark	<1997	0-17	PCR	Oral rinses	392	0.26%
Puranen 1996	Finland	1981-96	0.3-11.6	PCR	Oral scrapings	98	31.6%
Rice 1996	London	<1996	3-11	PCR	Buccal swabs	267	17%
Jennison 1990		<1990	preschool	PCR	Oral scrapings	21	24%

Table 2: Frequency with which high-risk HPV types were detected in tonsillectomy samples using PCR methods (> 10 cases).

Study	Year	City	Period of patient accrual	Age range	HPV detecti on	Number of samples	Number positive for HPV
Klinkenberg	2010	Netherlands	1997-98	29.2	PCR	195	2 (1%)
Ernster	2009	USA	1979-82; 1997- 2001	> 21 years	PCR	226	0 (0%)
Kim	2007	Korea	1995-2005	NS	RT-PCR	69	3 (4%)
Sisk	2006	USA	AO	paediatric patients	PCR	50	1 (2%)
Ribeiro	2006	Brazil	NS	2-13 years	PCR	64	5 (7.8%)

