Mammas	2006	Greece	1995-2000	2-14 years	PCR	106	6 (5.7%)
Chen	2005	Sweden	2001-02	23.2 years	PCR	206	13 (6.3%)
Strome	2002	USA	1987-95	52.5 years	PCR	48	0 (0%)
Klussman	2001	Germany	"new cases"	52 years	PCR	14	0 (0%)

AO (abstract only): includes unspecified number of low-risk types; prevalence fell with increasing age from 11.5% in preschool children to 0% in older adults.

NS: Not Significant.

This data is essential for the assessment of the need for and cost effectiveness of including boys in the HPV vaccination programmes, and for the determination of the age of viral acquisition in the general population and hence the age of start of vaccination programmes (Kim,Vaccine 2008; Smith Pediatr Infect Dis J. 2007), as it may be that young people acquire earlier in the mouth than in the cervix, due to oral sex experimentation starting at a younger age than sexual intercourse. This data is also essential for the evaluation of the potential effectiveness of screening programmes, and preventative educational programmes (Pediatr Infect Dis J. 2007).

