7. STUDY PROCEDURES AND SAMPLE COLLECTION

All samples should be collected in accordance to the study procedure manual developed by GSK with details of sample collection kits, volume of samples to be collected and storage temperature requirements.

For a patient to be eligible for inclusion in the data analysis, the following samples are a minimum requirement:

- Oral samples
- Blood
- Oropharyngeal brushings
- Tonsils

 After written consent is obtained, the patients (above 16 years old only) will complete a short study questionnaire including age, gender, history of tobacco/alcohol use, sexual history including age of start of sexual intercourse, lifetime numbers of sexual partners, engagement in oral sex and lifetime number of oral sex partners etc.

- 2. An HPV vaccination history will also be taken. Consent/assent will also be taken from the patient, parent(s) or their guardian(s), if applicable, to obtain the patient's HPV vaccination status from vaccine and medical health records from their GP and/or other relevant health and educational authorities. The data requested will include confirmation of HPV vaccination status, including dates, number of doses and the type of vaccine given.
- 3. Oral fluid samples will be collected for HPV PCR and HPV antibody tests, using an oral rinse and an exudate collection device respectively.
- 4. A 20 30 ml urine sample will be collected for HPV PCR test.
- 5. Blood serum will be taken for HPV and biomarker serology tests. This can be taken after the patient has been anaesthetised if necessary. 20 mls of blood will be taken from patients aged 16 years and above, 10 mls from patients below 16 years old.
- 6. Once the patient is anaesthetised, two brush cytology scrapings using cytobrushes (provided) will be taken: one from the posterior pharynx including above and below the soft palate so that the adenoidal area is included, and a second separate brush scrape will be taken from the back of the tongue (base of tongue).
- 7. Tonsillectomy will then be performed and the tonsillar tissue will be placed in 10% buffered formalin and sent to the pathology department for paraffin embedding according to a specific protocol.
- 8. Stratified sampling will be employed to ensure that sufficient numbers of patients are recruited from all age groups, especially the age groups between 10 and 20 years old.

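### Section 12.3 ties age of acquisition to a single cut at age 14, with a non-exposed label the protocol's own background contradicts and a cohort share that Table 6 does not give

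*Protocol*

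**What the plan says.** Section 12.3 divides the cohort into "those aged 14 and under (non-exposed, approximately one third of the cohort), and patients over 14 years of age (exposed"). The stated purpose is "to allow the determination of the age of acquisition of infection and the optimal age of start of vaccination". The planned total is 925, and Table 6 in the same section sets eight age strata, with 150 patients in each five-year band up to age 24.

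The background describes children differently. Section 1.2 says: "Other bodily fluids e.g. saliva may potentially also be routes of transmission, especially before the onset of sexual activity". In section 1.4, Table 1 gives oral prevalence by age in one study as "8.7% <7yrs, 0% 7-12, 5.2% 13-20". Other rows of Table 1 give 31.6% at 0.3-11.6 years and 17% at 3-11 years. Table 2 gives tonsil rates of 7.8% at 2-13 years and 5.7% at 2-14 years, and its note says that "prevalence fell with increasing age from 11.5% in preschool children to 0% in older adults".

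Section 12.2.1 plans prevalence with exact confidence intervals by age and gender group. It also plans a logistic model with continuous age (one to three degrees, possibly transformed), gender and centre. Neither is named as the source of the age of acquisition.

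**The concern.** Calling everyone up to 14 non-exposed makes that group a clean baseline, so that any excess above 14 reads as acquisition. If infection is present in early childhood, low in mid-childhood and higher in the teens, pooling ages 0-14 averages the early positives with the trough. The contrast can then be flat or reversed although prevalence rises in the early teens. Even when it works, it says only that prevalence differs on the two sides of 14, not at what age infection begins.

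Section 12.3 attaches a policy conclusion, when vaccination should start, to this comparison. Vaccination complicates it further. Section 12.2.2 puts the female target age at 12 to 24, so vaccinated patients can fall on both sides of the cut, and mostly above it. Lower prevalence there may reflect the vaccine rather than an absence of acquisition.

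**Working it through.** **1. The stated share.** Table 6: (150 + 150 + 150)/925 = 450/925 = 48.6%. One third of 925 would be about 308. The percentages printed in Table 6 also add to 3 × 16.5 = 49.5%. The caption of Figure 1 still refers to 1250 patients, and 450/1250 = 36%, which is closer to a third. The interval in the same section (8.4 to 11.8% at 10% observed) reproduces with n = 1250 (exact 8.39 to 11.80%) but not with n = 925 (8.1 to 12.1%). The phrase is probably left over from a target of 1250; that is an inference.

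**2. The label.** Pooling the three paediatric rows of Table 2: (1 + 5 + 6)/(50 + 64 + 106) = 12/220 = 5.5%, exact 95% CI 2.8 to 9.3%. Without the abstract-only study, which includes low-risk types: 11/170 = 6.5% (3.3 to 11.3%). Neither fits a near-zero baseline.

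**3. What the contrast would show.** Inputs: the Table 1 pattern (8.7% under 7, 0% at 7-12, 5.2% at 13-20), Table 6 sizes, and two-sided alpha 0.05 (section 12.2). Assumptions: ages uniform within bands, and prevalence *a* above age 20, which that study does not cover. I vary *a* over the 0% to 10% that section 12.3 gives for oral HPV.

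Aged 14 and under:
- 0-4: 8.7%
- 5-9: (2 × 8.7 + 3 × 0)/5 = 3.48%
- 10-14: (3 × 0 + 2 × 5.2)/5 = 2.08%
- expected positives 13.05 + 5.22 + 3.12 = 21.39; 21.39/450 = 4.75%

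Over 14 (n = 475):
- 15-19: 150 × 5.2% = 7.80
- 20-24: 150 × (5.2% + 4*a*)/5 = 1.56 + 120*a*
- 25 and over: 175*a*
- prevalence = (9.36 + 295*a*)/475

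Power = Φ((d − 1.96·SE0)/SE1) + Φ((−d − 1.96·SE0)/SE1), where d is the absolute difference, SE0 the pooled and SE1 the unpooled standard error. At *a* = 5.2%, d = 0.0045 and SE0 ≈ SE1 ≈ 0.0143, so power = 0.049 + 0.011 ≈ 6%.

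| Assumed above 20 | Over 14 | 14 and under | Direction | Power |
|---|---|---|---|---|
| 0% | 1.97% | 4.75% | older lower | 65% |
| 2% | 3.21% | 4.75% | older lower | 23% |
| 5.2% | 5.20% | 4.75% | near null | 6% |
| 6.5% | 6.01% | 4.75% | older higher | 13% |
| 10% | 8.18% | 4.75% | older higher | 56% |

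The groups are equal at *a* = (0.04753 × 475 − 9.36)/295 = 4.5%. Below that the contrast is reversed, and the 65% in the first row is power to declare the reversed difference.

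**4. The rise in the same pattern.** Ages 7-12 number 6 × 30 = 180 at 0%. Ages 13-20 number 60 + 150 + 30 = 240 at 5.2%. Power is about 91% by the normal approximation and 99% by simulated Fisher test.

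**5. The planned age model.** In 300 simulated cohorts with *a* = 5.2%, the likelihood-ratio test of any age effect was significant in 11% (linear), 18% (quadratic) and 48% (cubic), against about 6% for the two-group Fisher test.

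**The case against.** The strongest reply is that the sentence in 12.3 only justifies the sampling. Section 12.2 contains no test at age 14, and 12.2.1 plans prevalence by age group and a continuous-age model whose form may be non-linear. Figure 2 shows precision for groups of 100, 150 and 250, so band-level estimates are intended. This stands. A reader might infer that age of acquisition can be seen only in the two-group contrast; the documents do not support that. But 12.3 is the one place that says how age of acquisition will be determined, and it names the contrast. The model in 12.2.1 is exploratory and lists gender and centre but not vaccination status. Vaccination status is a candidate covariate only in the risk-factor models of 12.2.2, and 12.4 removes vaccinated women only from the historical comparison.

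The second reply is that the near-null result uses one oral-sample study of 268 people under 20, whereas the primary outcome is HPV in tonsils. Other Table 1 rows differ: 0.26% at 0-17 years and 1.9% at 2-20 years suggest low rates throughout, while 17% at 3-11 years suggests no mid-childhood trough. The Table 2 note describes a fall with age, not a teenage rise. This also stands. A reader might infer that the contrast is bound to miss the rise, but that depends on the pattern. If children are near 0% and older patients clearly higher, it will show a difference.

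A reader might also infer that equal bands contradict section 7, which asks for enough patients in "especially the age groups between 10 and 20 years old". They do not: section 7 asks for sufficient numbers, and ages 10-19 go from 17/59 = 28.8% in Table 5 to 300/925 = 32.4% in Table 6.

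**Conclusion.** The point holds in a limited form. Three parts need no assumed prevalence: the non-exposed label conflicts with the protocol's own background, a single cut cannot locate an age, and the share aged 14 and under is 48.6%, not about a third. If non-exposed was meant as sexually unexposed only, the group still cannot serve as an uninfected baseline.

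That the contrast may hide or reverse a teenage rise is conditional. It rests on one oral-sample pattern, uniform ages within bands and an assumed rate above 20. On those terms the contrast has about 6% power at 5.2% above age 20, and it is reversed below about 4.5%. The plan's other age analyses can still reveal the rise, so the fault lies in which analysis carries the conclusion. It should be corrected, but it does not put the prevalence estimates themselves at risk.

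**What to change.** In section 12.3:
- Remove the exposed and non-exposed labels, and stop using the two-group contrast as the basis for age of acquisition.
- Base that conclusion on the continuous-age logistic model of 12.2.1, with non-linear terms allowed, together with prevalence and exact confidence intervals across the Table 6 bands.
- Do this in HPV-unvaccinated patients, or adjust for vaccination status.
- Report ages 0-4 separately, as early-life infection.
- Set no fixed reference band. Ages 5-9 look natural, but under the pattern above that band averages 3.5%, and comparing it with 15-19 (5.2%, 150 each) has only about 11% power.
- Correct the stated share to about 49% (450/925).

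The cost is wording in the protocol and analysis plan; the protocol already provides for collecting the data, including vaccination status. The drawback is precision: age-specific estimates from about 150 patients per band are less precise than one pooled contrast, and more so once vaccinated females are excluded. At 5% observed, the exact interval is about 2.3 to 10.2% for n = 150, against about 3.1 to 7.3% for n = 450.
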